7.3.6 Laboratory Parameters

Clinical laboratory results, including hematology (WBC, RBC, hemoglobin, hematocrit, mean corpuscular volume, mean corpuscular hemoglobin, red cell distribution width, platelets, neutrophils, lymphocytes, monocytes, eosinophils and basophils), blood chemistry (phosphorus, calcium, sodium, chloride, bicarbonate, potassium, fasting blood glucose, creatine phosphokinase, lactate dehydrogenase), kidney and liver function tests (creatinine, blood urea nitrogen, uric acid, alanine aminotransferase (ALT), aspartate aminotransferase (AST), total bilirubin, alkaline phosphatase, total protein, albumin, gamma glutamic transpeptidase, cholesterol), coagulation (prothrombin time and partial thromboplastin time) urinalysis (color, appearance, specific gravity, pH, protein, glucose, ketones, blood, bilirubin, microscopy), and urine pregnancy test (for females of childbearing age) will be listed for each patient and visit in the patient profiles. Individual lab values will be flagged as 'High' or 'Low' if outside the clinical site's normal ranges. A summary of the number of patients with abnormal and/or clinically significant laboratory values will be provided. The following laboratory values and thresholds will be highlighted to indicate their clinical significance for major functions:

- WBC above 2ULN (upper limit of normal)
- Neutropenia < 1500
- Platelets < 100,000
- Creatinine > 1.5ULN
- ALT \geq 3ULN
- AST \geq 3ULN
- Total bilirubin \geq 2 ULN

The lab values will be graded by site physicians, and clinically significant abnormal lab values will also be recorded as AEs.

7.3.7 Vital Signs

Vital signs will be summarized and also listed by cohort and visit. In addition, patients' vital signs at each study visit will be listed with other examination results in a patient profile. Any abnormalities or clinically significant changes in patients' vital signs will be indicated.

7.3.8 Concomitant Medications

Concomitant medications including the WHO drug coding will be listed by patient, cohort and study visit.

7.3.9 Physical Examinations

Physical examinations will be conducted at Day -28 and Week 48 visits. System abnormality frequencies and percentages (including head/ear-nose-throat, respiratory, gastrointestinal, cardiovascular, musculoskeletal, neurologic, endocrine/metabolic, lymphatic/hematologic, dermatologic, psychological and genitourinary) will be tabulated by cohort at each time point. Clinically significant changes, occurring if an assessment was normal at Day -28 but is abnormal at Week 48, in physical examination assessments from Day -28 to Week 48 will be indicated.

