3 STUDY DIAGRAM

4 INTRODUCTION AND RATIONALE

Usher syndrome is characterized by sensorineural hearing loss and retinitis pigmentosa (RP). It accounts for the majority of the deaf-blindness population and between 8-33% of individuals with RP (1). The disease is named after the British ophthalmologist Charles Usher, who examined the pathology and transmission of the illness in 1914 on the basis of 69 cases (2). The prevalence of Usher syndrome ranges from 3.6 to 6.2 per 100,000 in the US and European populations (3, 4, 5, 6, 7).

Usher syndrome is inherited in an autosomal recessive pattern and is classified into subtypes called Usher 1, 2 and 3 in order of decreasing severity of deafness. Usher 1 and 2 are the more common forms. People with Usher 1 syndrome are congenitally profoundly deaf and have vestibular dysfunction as well as prepubertal onset of retinitis pigmentosa leading to blindness. Babies with Usher syndrome Type 1 are usually slow to develop motor skills such as walking.

Usher syndrome Type 1B which accounts for 30-50% of Usher syndrome Type 1 (prevalence of ~1 per 100,000 people in the population [3, 4, 5]) is caused by a mutation in the gene coding for the unconventional myosin (motor) protein (MYO7A [8]). Myosin VIIa is expressed in the hair cells of the cochlea in the ear and the retinal pigment epithelial and photoreceptor cells of the retina, two tissues known to be affected in Usher syndrome Type 1B patients (9, 10). In addition, myosin VIIa is also expressed in the olfactory epithelium, brain, choroid plexus, intestine, liver, kidney, adrenal gland, testis, and lymphocytes (11). In the ear, myosin VIIa plays a role in the development and maintenance of inner ear structures such as hair cells (stereocilia) which transmit sound and motion signals to the brain. Loss of normal myosin VIIa function leads to disorganized development of the hair cell structure causing congenital profound deafness and vestibular dysfunction. While the molecular basis of retinal degeneration in Usher syndrome Type 1B patients is not completely understood, loss of normal myosin VIIa function leads to photoreceptor degeneration from the outer periphery to the macula.

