11 OBLIGATIONS OF THE INVESTIGATOR REGARDING SAFETY REPORTING

11.1 ADVERSE EVENT DEFINITION

An adverse event (AE) is any untoward medical occurrence in a patient that develops or worsens in severity during the conduct of a clinical study of a pharmaceutical product and does not necessarily have a causal relationship to the investigational product. This can, therefore, be any unfavorable and unintended physical sign, symptom, or laboratory parameter that develops or worsens in severity during the course of the study, whether or not considered related to the investigational product.

All AEs must be described in the appropriate section of the CRF and their seriousness and putative relationship (causality) to the study medication and/or protocol procedures noted. Adverse events are recorded following signature of the informed consent; this is to ensure that any adverse events associated with the screening procedures are captured.

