5.0 ENDPOINTS

5.1 Primary Endpoints

The primary objective of this study is evaluation of safety and tolerability of ascending doses of UshStat in patients with Usher syndrome type 1B. Safety and tolerability of the IMP will be evaluated using the following endpoints:

- The incidence of AEs over a 12-month period following a single intraocular dose of UshStat.
- Clinically important changes from baseline (Day -28) in the following safety assessments:
 - Best-corrected visual acuity (BCVA)
 - Slit-lamp examination
 - Indirect ophthalmoscopy
 - Fundus photography
 - Intraocular pressure (IOP)
 - Ocular coherence tomography (OCT)
 - Laboratory parameters
 - Vital signs
 - Concomitant medications
 - Physical examinations

For all primary endpoints with repeated measures, the primary time point will be considered the Week 48 (12-month) visit unless otherwise specified. BCVA and perimetry measurements are subject to broad intra-individual variability therefore the baseline value used for these measures will be an average of all the values obtained during the screening period.

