7.3.1 Adverse Events

AEs will be coded using MedDRA® (last version available at time of database lock). All reported events for all patients with cohort, event description, event date, resolution date, severity, outcome, relatedness, SAE indication, duration, High Level Term (HLT), System Organ Class (SOC), and Preferred Term (PT) will be listed. Specifically, AEs prior to treatment, treatment emergent adverse events (TEAEs), (i.e., started or increased in severity after the patient receives IMP, including abnormal lab results, ECG, etc.) and TEAEs of special interest will be listed separately. An overall summary table of TEAEs will also be provided that includes the number and percentage of TEAEs and patients with at least one TEAE in each dose cohort with:

- A fatal AE (death)
- At least one serious AE
- At least one severe AE
- At least one AE related to IMP
- At least one TEAE related to procedure
- Without any AEs

In addition, tables will present both the number and percentage of TEAEs and patients with TEAEs by SOC, HLT, PT, severity and cohort. Adverse events of special interest (AESI), detailed in the protocol, will be summarized by SOC, HLT, PT, severity and cohort. AESIs will be indicated, where appropriate in the patient profile listing of AEs. AEs related to the IMP and serious adverse events (SAEs) will be indicated in the AE listing and described in detail in the body of the report. Specific grouping will be done for events inflammatory in nature in the eye. Summary tables will be presented both with the inflammatory events grouped and without the events grouped. All events with the following preferred terms will be considered inflammatory in nature in the eye:

- Anterior chamber cell
- Anterior chamber inflammation
- Choroidal effusion
- Conjunctivitis
- Eye inflammation
- Eye discharge
- Keratitis

- Macular oedema
- Subretinal fluid
- Uveitis
- Vitreous floaters

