8.2 Baseline Characteristics

Table 2A will summarize Baseline demographic information for all patients and stratify the information by cohort.

Table 2A: Demographics Summary by Cohort

		Enrolled Patients (N=X)	Cohort 1 (N=X)	Cohort 2 (N=X)	Cohort 3 (N=X)	Cohort 4 (N=X)	Cohort 5 (N=X)
AGE (years)	Median (Range)	X (X-X)	X (X-X)	X (X-X)	X (X-X)	X (X-X)	X (X-X)
GENDER	Female	N (%)	N (%)	N (%)	N (%)	N (%)	N (%)
	Male	N (%)	N (%)	N (%)	N (%)	N (%)	N (%)
RACE	American Indian or Alaskan Native	N (%)	N (%)	N (%)	N (%)	N (%)	N (%)
	Asian	N (%)	N (%)	N (%)	N (%)	N (%)	N (%)
	Black or African American	N (%)	N (%)	N (%)	N (%)	N (%)	N (%)
	Native Hawaiian or other Pacific Islander	N (%)	N (%)	N (%)	N (%)	N (%)	N (%)
	Other	N (%)	N (%)	N (%)	N (%)	N (%)	N (%)
	White	N (%)	N (%)	N (%)	N (%)	N (%)	N (%)
	Hispanic or Latino	N (%)	N (%)	N (%)	N (%)	N (%)	N (%)
ETHNICITY	Not Hispanic or Latino	N (%)	N (%)	N (%)	N (%)	N (%)	N (%)
	HEIGHT (cm)	Median (Range)	X (X-X)				
WEIGHT (kg)	Median (Range)	X (X-X)	X (X-X)	X (X-X)	X (X-X)	X (X-X)	X (X-X)

Table 2B will list demographic information by patient.

Table 2B: Detailed Demographic Listing by Cohort

Patient Cohort	Patient ID			Age	Gender	Race	Ethnicity	Height (cm)	Weight (kg)

Table 2C will give a summary of individual patient medical history. Further detailed table(s) may be provided where appropriate.

Table 2C: General Medical History by Patient

Patient ID	Exam Date	Cardio-vascular	Hematology/ Oncology	Psych- iatric	Gastro- intestinal	Neurologic	Endocrine	Nephrologic	Resp- iratory	Autoimmune	Musculo- skeletal	Allergies	Non-Ocular Surgery

Table 2D will summarize Baseline physical examination parameters for all patients by cohort. Individual patient profiles will also include physical examination information, laboratory values, vital signs, etc. at Baseline as well as during follow-up. See Section 9 for patient profile examples.

Table 2D: Baseline Physical Examination Parameters by Cohort

		All Eligible Patients	Cohort 1	Cohort 2	Cohort 3	Cohort 4	Cohort 5
Cardiovascular Assessments	Normal	N (%)	N (%)	N (%)	N (%)	N (%)	N (%)
	Abnormal	N (%)	N (%)	N (%)	N (%)	N (%)	N (%)
Dermatologic Assessments	Normal	N (%)	N (%)	N (%)	N (%)	N (%)	N (%)
	Abnormal	N (%)	N (%)	N (%)	N (%)	N (%)	N (%)
Endocrine/Metabolic Assessments	Normal	N (%)	N (%)	N (%)	N (%)	N (%)	N (%)
	Abnormal	N (%)	N (%)	N (%)	N (%)	N (%)	N (%)
GI Assessments	Normal	N (%)	N (%)	N (%)	N (%)	N (%)	N (%)
	Abnormal	N (%)	N (%)	N (%)	N (%)	N (%)	N (%)

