MEAN PEAK AMPLITUDES AND LATENCIES AT BASELINE (mfERG)															
	Amplitude (nV/deg ²) - max+min Latency (ms)														
	Ring 1		Ring 2		Ring 3		Ring 4		Ring 5		Ring 6		Comments		
Visit	Study	Fellow	Study	Fellow	Study	Fellow	Study	Fellow	Study	Fellow	Study	Fellow	Study	Fellow	
COMMENTS:															

COMMENTS

[figure not shown]
SUMMARY CLINICAL OBSERVATIONS

OVERALL CONCLUSIONS

Visual Acuity

Intraocular Pressure (IOP)

ADMINISTRATION OF INVESTIGATIONAL PRODUCT					
Surgery Date	Full Dose Administered	Fluid-air Exchange Performed	Air Bubble Removed	Procedure Resulted in Retinal Tear	Complication(s) During Surgery
COMMENTS:					

PHYSICAL EXAM										
	Lymphatic/Hematologic		Musculoskeletal		Neurologic		Psychologic		Respiratory	
Visit	Abnormalities	Change from Baseline	Abnormalities	Change from Baseline	Abnormalities	Change from Baseline	Abnormalities	Change from Baseline	Abnormalities	Change from Baseline
COMMENTS:										

LENS ASSESSMENT									
		Natural Lens		Nuclear Score		Cortical Score		PCS Score	
Visit	Visit Date	Study	Fellow	Study	Fellow	Study	Fellow	Study	Fellow
COMMENTS:									

FUNDUS PHOTOS TDU Study													
	Treatment Efficacy		Increased Inflammation		Hemorrhage		Reported AE		Retinal Detachment		Comments		
Visit	Study	Fellow	Study	Fellow	Study	Fellow	Study	Fellow	Study	Fellow	Study	Fellow	
COMMENTS:													

NOTE: For Laboratory Listings, Yellow Indicates Outside of Site's Normal Laboratory Reference Range

²Neutrophil totals were not collected until September 2014

³ RDW-CV values were converted from RDW-SD values

KIDNEY AND LIVER FUNCTION												
	Kidney Function			Liver Function								
Visit	Creatinine (umol/L)	BUN (mmol/L)	Uric Acid (umol/L)	ALT (U/L)	AST (U/L)	Total Bilirubin (umol/L)	Alkaline Phosphatase (U/L)	Total Protein (g/L)	Albumin (g/L)	GGT (U/L)	Cholesterol (mmol/L)	
COMMENTS:												

Concomitant Medications									
Start Date	Action Date	Action	Medication Name	Indication	Route	Dose	Units	Schedule	Result of AE

Comments:

**SAR421869 TDU13600
COORDINATING CENTER**

August 30, 2019

[figure not shown]
Subject: **Table of Contents for Final Tables, Listings and Figures (TLFs) – SAR421869
Protocol TDU13600**

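### The SAP 7.3.9 flag for physical examination change omits a worsening, or a new finding, in any body system already abnormal at Day -28

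*SAP*

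**What the plan says.** SAP Section 5.1 places physical examinations under the primary endpoint item "Clinically important changes from baseline (Day -28) in the following safety assessments", and Protocol Section 6.1 does the same. Section 7.3.9 of the SAP schedules the examination at Day -28 and Week 48. It names eleven body systems, among them "head/ear-nose-throat, respiratory, gastrointestinal, cardiovascular, musculoskeletal, neurologic, endocrine/metabolic", and plans a tabulation of abnormality frequencies by cohort at each of the two time points. It then says which changes will be indicated: "Clinically significant changes, occurring if an assessment was normal at Day -28 but is abnormal at Week 48, in physical examination assessments". No other transition is named.

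The only physical examination summary shell in SAP Section 8 is "Table 2D: Baseline Physical Examination Parameters by Cohort". It gives each system two rows, normal and abnormal, with no severity grade.

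On the population, Protocol Section 4 states: "People with Usher 1 syndrome are congenitally profoundly deaf and have vestibular dysfunction".

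**The concern.** The rule treats a clinically significant change as identical to a shift from normal to abnormal. A system that starts abnormal cannot make that shift, whatever happens to it later. The rating is per system, so the omission is wider than progression of the same condition. An unrelated new finding in a system already rated abnormal is also passed over. This applies to any patient with any baseline abnormality in any of the eleven systems.

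The Usher population makes it more than theoretical. If a site records congenital deafness or vestibular loss as an abnormal examination, head/ENT, and perhaps neurologic, is abnormal from the start. For those patients, the absence of a flag in these systems follows from the definition and says nothing about safety.

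**Working it through.** No sample size, power or error rate is involved, and the plan states no figure to reproduce. The check is to apply the rule to every possible case, and then to trace where an unflagged worsening would otherwise appear.

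**Step 1: the rule applied to the two-level rating** (SAP 7.3.9; Table 2D shell in SAP 8.2).

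| Day -28 | Week 48 | Flagged under 7.3.9? |
|---|---|---|
| Normal | Normal | No |
| Normal | Abnormal | Yes |
| Abnormal | Normal | No |
| Abnormal | Abnormal, including worse or with a new finding | No |

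The planned frequencies do not recover the last row. A patient rated abnormal on both occasions adds one to the abnormal count each time, so the net difference is 1 - 1 = 0.

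**Step 2: how many patients are affected.** Let q be the share of patients rated abnormal in a given system at Day -28. Only the remainder can be flagged for that system:

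share that can be flagged = 1 - q

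- q = 0: 1 - 0 = 100%
- q = 0.5: 1 - 0.5 = 50%
- q = 1: 1 - 1 = 0%

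The documents give no value of q for head/ENT or neurologic, so the whole range stays open. In a cohort of three, as in the table shell of the August 2019 memorandum attached to the SAP, each patient abnormal at baseline takes 1/3 = 33% of the cohort out of the flag's reach for that system.

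**Step 3: where else a worsening could appear.**

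- *Adverse events.* Protocol 11.1 covers a sign or symptom that "develops or worsens in severity during the course of the study, whether or not considered related to the investigational product". SAP 7.3.1 counts as treatment-emergent an event that "started or increased in severity after the patient receives IMP, including abnormal lab results, ECG, etc". Both include worsening. Protocol 13.4.6, which deals with physical examination specifically, sends only new abnormalities to the adverse event summary, so a worsening relies on the general definition.
- *Patient profiles.* The physical examination shell in SAP Section 9 has, for each system shown, an abnormalities column and a "Change from Baseline" column. Neurologic is among the systems shown. I could not see head/ENT in the text available, which may be a loss in text extraction. SAP 7.3.9 does not refer to these columns.
- *Final outputs.* The 2019 memorandum lists a baseline physical examination table (2F) and a by-patient listing of abnormal examinations (Listing CC), whose shell is not given. No title names a Week 48 or change table for physical examination. Patient profiles are not on the list, and the memorandum does not say whether they will be produced.

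**The case against.** The strongest reply is that 7.3.9 is a display convention and not the trial's main safety net. Adverse event incidence is the first-named primary endpoint. A physician reviews adverse events at every visit (Protocol 9.3.12), whereas the physical examination is scheduled only at Day -28 and Week 48. This stands. A reader might infer that deterioration of hearing or balance could never surface in the trial's safety results; the adverse event definitions and the profile columns contradict that.

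The reply also holds on three narrower points.

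- The documents do not say how examiners rate a stable congenital deficit, or that the examination tests hearing or balance. Known conditions also have their own place in the medical history tables. A reader might count head/ENT and neurologic as one or two of eleven systems (1/11 = 9%, 2/11 = 18%) and take that as the share of assessments lost. That is a count of list items; it assumes every patient starts abnormal.
- The adverse event definition governs adverse event reporting. Nothing obliges 7.3.9 to match it, so the difference is not in itself an inconsistency.
- A reader might also object that the rule calls any minor new finding clinically significant. Over-flagging is the cautious direction in a small descriptive safety study, so this is a preference and not an error.

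None of this changes what the flag does. Adverse events are a separate item within the primary endpoint, and the other routes do not supply what 7.3.9 leaves out of its own item.

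**Conclusion.** The point holds for the 7.3.9 flag. As written, the rule cannot register a worsening or a new finding in a system already abnormal at Day -28, and this component of the primary safety endpoint is incomplete to that extent. The omission follows directly from the stated rule and the two-level rating.

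Its extent cannot be stated from the documents. For head/ENT or neurologic the share of patients out of reach lies between 0% and 100%. That these systems are the likely ones rests on two assumptions: that sites rate the congenital deficit as abnormal, and that vestibular findings are placed under neurologic. The second is less certain.

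The consequence is limited. The analysis is descriptive, and a worsening can still be reported as an adverse event or be visible in a patient profile or, depending on its content, Listing CC. It is a modest defect, worth correcting because the rule is explicit and the correction is cheap.

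**What to change.** Reword SAP 7.3.9 along these lines:

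*A physical examination change is flagged if (a) a system rated normal at the last pre-surgery examination is abnormal at Week 48, or (b) a system rated abnormal at the last pre-surgery examination has a new or worsened abnormality at Week 48, as recorded in the abnormalities and change columns of the patient profile. The two kinds of change are shown separately.*

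The last pre-surgery examination follows the general baseline rule in Protocol Section 6. It differs from Day -28 only where the examination was repeated, for example at re-screening. Because Protocol 6.1 and SAP 5.1 still label baseline as Day -28, the label should be aligned at the same time.

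Two checks go with the rewording: that the profile shell carries these columns for all eleven systems, head/ENT included, and that the profiles, or a Listing CC with the same fields, are part of the final outputs.

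Investigator-rated clinical significance can be added where the case report form already records it. The documents do not show that it is collected for each examination change, so the flag should not depend on it.

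The cost is a short SAP revision and a small amount of extra listing review. If the profile fields are populated as the shell shows, no new data are needed.

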7.4 Secondary Endpoints

The secondary endpoints include changes in the study eye from Day -28 to Weeks 24 and 48 in function relative to the untreated, contralateral eye in several visual function measures. The primary endpoints of BCVA, ocular inflammation and OCT will also serve as secondary endpoint measures. Analysis of these parameters will be conducted as outlined in [Sections 7.3.2, 7.3.3](#) and [7.3.5](#), respectively.

